5.4 Inclusion/Exclusion Criteria

Aims 1 and 2:

For the nurse portion of the trial, 1 inpatient hospital unit at Ann Arbor VAMC and 2 units at MEDVAMC will be randomized to receive the intervention and an equal number of units at each site will be randomized to receive the control. All nurses on the selected units will be asked to participate in the voluntary study. Inclusion criteria are all nurses on the identified units. There are no exclusion criteria.

For the physician portion of the trial, we will focus on inpatient physician teaching teams, which typically include 1 attending physician, 1 senior resident, and 2-3 intern physicians (Year 1 residents). Inclusion criteria are physicians on inpatient medical teams. Exclusion criteria are medical students, surgical attendings, and physicians on sub-specialty teams. Attending physicians may be on service multiple times per year. Attending physicians will be allowed to participate in multiple months, however, once a physician has been randomized to the intervention arm, they will no longer be eligible to participate in the control arm of the study.

Aim 3:

In this aim we will conduct a qualitative evaluation to better understand the perception of the intervention and assess any barriers or facilitators encountered. The primary subjects will be nurses and physicians that participated in the intervention. Inclusion criteria for this aim is being a nurse or physician that participated in the intervention. There are no exclusion criteria.

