5.0 Study Procedures

5.1 Study Design

Research Design: A multi-center, repeat-measures randomized controlled mixed-methods trial.

Study Population: The proposed study will focus on Internal Medicine physicians who are part of inpatient care teams and nurses providing care on medical and medical/surgical units at LTC Charles S. Kettles VAMC in Ann Arbor, MI and MEDVAMC in Houston, TX. Medical students, surgical physicians, and physicians on sub-specialty teams will not be included. At both participating facilities the inpatient care teams are predominately composed of 1 attending, 1 senior resident, 2 interns, and up to 3 medical or physician assistant students. Interns and senior residents are usually assigned to a team for 4-week blocks (occasionally 2 weeks), while attendings rotate approximately every 2 weeks. The Ann Arbor VAMC has 3 medical or medical/surgical inpatient units, while MEDVAMC has 5 units. At both facilities each nursing unit employs between 20-30 nurses. We will aim to recruit approximately 30 attendings, 72 residents and 40 nurses at Ann Arbor VAMC. As MEDVAMC is larger, with a greater number of inpatient care teams and nursing units than the Ann Arbor VAMC, we will aim to recruit approximately 40 attendings, 72 residents and 90 nurses. Our target study sample size is a total of 344 physicians and nurses (167 intervention/177 control). For Aim 3, we plan to interview approximately 8 physician team members and 4-6 nurses from the intervention arm at each site.

General Study Overview and Outcome Measures:

A summary of the proposed study activities at each participating site is presented in **Table 2** below.

Table 2: Overview of Study Activities at Each Study Site

| Study Detail | Physicians | Nurses |
|----------------------------------|--|--|
| Target | Attendings, senior residents and interns on inpatient medicine teams | Nurses on medical or medical/surgical units |
| Teams/Units Participating | 2 teams each month for 12 months randomized to intervention or control arm at each site | 2 units (1 intervention; 1 control) at Ann Arbor VAMC & 4 units (2 intervention; 2 control) at MEDVAMC randomized once & followed for 12-months |
| Estimated number of participants | 107 intervention and 107 control | 20 intervention and 20 control at Ann Arbor VAMC; 40 intervention and 50 control at MEDVAMC |
| Habituation Period | 1 month | 1 month |

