Randomization – At each study site the participating physician teams and nursing units will be randomly assigned into one of two study arms (intervention/control). For physician teams, this will occur on a rolling basis for 12 months with 2 physician teams randomly selected at each site each month for participation (1 intervention, 1 control). Once randomized, an email will be sent to the initial attending of the team introducing the study and asking them to reply to the email if they would prefer to opt out and not have their team participate in the randomized controlled trial. If the attending physician from a team refuses to allow their team to participate, the next team identified from the randomized list will be approached to participate. If a new attending joins the team mid-month, they will be approached to participate in the study, but will be automatically assigned to the same randomization group as the rest of their team.

Similarly, a total of 2 medical/surgical units from VAAHS (1 intervention, 1 control) and 4 medical/surgical units from MEDVAMC (2 intervention, 2 control) will be randomly selected to participate in the nurse portion of the project. The nurse manager for each

selected unit will then be approached to obtain approval for the unit to participate. If a nurse manager declines, the next unit on the list will be selected.

For both physicians and nurses, an independent statistician will allocate the teams and units in a concealed fashion, using a computer-generated randomization schema. The physicians and nurses from the intervention groups will receive both independent and group-facilitated mindfulness education, will be encouraged to use a mindfulness mobile app as a practice reminder and additional resource, and instructed to integrate moments of mindfulness with repeated episodes of hand hygiene during the course of caring for patients. The control groups will receive no such education or intervention and will continue as usual.

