that service rotation on weekdays (3-4 weeks). For the physician teams, which rotate each month, this process will be repeated monthly for 1 year with up to 24 patient-care teams from each participating site. Nurses from both the intervention and control medical/surgical units will be observed for hand hygiene for one month. Observers will be blinded to randomization of the physician teams and thus intervention status. Since nurses remain assigned to one unit for a much longer period of time, nursing units will only participate once during the study. This will result in two nursing units from VAAHHS and four nursing units from MEDVAMC participating. At the completion of the observations, the physicians and nurses will again be asked to complete FFMQ, WBI, and select PSHW questions. To assess sustainability of well-being, mindfulness, and hand hygiene perceptions, we will ask participants to repeat FFMQ, WBI, and select PSHW questions at 6-month post-intervention follow-up points. To assess sustainability of hand hygiene among physicians, select hand hygiene observations at 3 to 12 months post-intervention (based on team schedules) will be conducted. To assess hand hygiene sustainability among nurses, unit-based hand hygiene practices will be reassessed at 1-year post-intervention. To examine changes across survey time points, crosswalk files will be utilized. Participant names will not be on the survey. A study team member will assign the survey respondents an identification number to link repeat surveys.

As part of the intervention we will also collect measures of fidelity. This will include information from the Mindfulness Coach/Mindfulness for Clinicians mobile application including usage and responses from any assessments included in the app about the participant's level of mindfulness. We will also collect data on completion of the Ohio State University STREAM Mind Body modules. This data will be completely de-identified. Both programs do not collect any personal identifiers. Instead, participants will be asked to register with a study assigned code. The de-identified user data for each code will be shared back with the study team to assess fidelity.

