 - Nurses on intervention units will be sent an introductory email (**Appendix J**) with information about the study and asking to set up a time and place to discuss the study in more detail. If we are unable to reach the nurses through email, study staff will approach the nurses during their work shift and ask to set up a time to meet to discuss the study in private. Recruitment will occur in a private room or office using the attached recruitment script (**Appendix K**).
- Physicians: We estimate enrolling approximately 35 attending physicians, 24 senior residents, and 48 intern physicians into each arm of the study, which will result in a total of 214 physicians in total. All physicians from physician teams will be asked to participate in the randomized controlled trial and provide a signed informed consent. Each month one team at the Ann Arbor VAMC and 2 teams at MEDVAMC will be randomized to intervention and an equal number at each site will be randomized to control. A flyer describing the study (**Appendix S**) will be emailed (**Appendix T**) to teaching attendings to introduce the study. Before the beginning of the month, the initial attending physician on each selected team will be sent an email describing the study and giving them the option to opt out of their team being approached to participate (**Appendix L**). A time and place will be scheduled to discuss the study in more detail and obtain informed consent from the attending (**Appendix M**). Unless the attending indicates they do not want their team participating, the rest of the team will be sent an email describing the study (**Appendix L**). Then study staff will approach the senior resident and interns in the team rooms and ask to speak with them about the study (**Appendix M**). If there are others in the team room, the study staff will ask the residents to follow them to a private room to discuss the study in greater detail. If they are willing to participate, they will be asked to sign an informed consent document. The primary participants are the attending physicians on each team. If the initial attending declines allowing their team to participate, another team will be randomly selected and approached for participation. If any physicians choose to not participate, they will not be asked to participate in the intervention activities (if randomized to the intervention) or to complete the study surveys (both study

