5.6 Data Analysis

Quantitative Statistical Analysis (Aims 1 and 2): Differences in hand hygiene adherence and duration between intervention and control groups will be assessed using Fisher's exact test and t-test, as appropriate. Risk differences in adherence to duration of hand hygiene will be calculated for both intervention and control groups. Because the primary outcomes for Aim 1 (i.e., hand hygiene adherence and duration) are expected to occur frequently, we will use generalized linear models to evaluate differences in hand hygiene adherence and duration for the intervention versus control group, with the Poisson distribution (log link) and robust error variance. Models will account for provider type and level, and will incorporate clustering by physician team (and separately for nursing unit). Statistical significance will be calculated for the intervention (intervention vs. control) coefficient.

As a secondary outcome for Aim 1, we will assess changes and differences in hand hygiene perception based on response to select questions from PSHW. For Aim 2, mindfulness will be based on responses to FFMQ and well-being will be based on responses to WBI. FFMQ and WBI scales will be scored according to the published algorithms. Descriptive statistics will be used to summarize participant scores from pre- and post-intervention, as well as 6-month post-intervention follow-up assessments. Within-group paired-samples t-tests will be used to test for improvement in participant scores across the baseline, post-intervention (~14 days for physicians and 1-month for nurses), and 6-month post-intervention follow-up periods, for the intervention and control groups separately. Analyses will use list-wise deletion for missing data. Participants not completing all surveys will still be included in any analysis for which they provide data. For all analyses, p values less than 0.05 will be considered significant and all tests will be two-tailed. Analysis of covariance (ANCOVA) models will then be used to assess relative changes in mindfulness, well-being, and hand hygiene perceptions across groups, the most direct test of discriminant validity. In these models, post-test scores will be predicted by group status controlling for pre-test scores.

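### A previously trained attending can supply control hand hygiene data, and the analysis neither tracks prior exposure nor links repeat blocks by the same attending

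*Protocol*

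**What the plan says.** **Eligibility (Protocol 5.4).** "Attending physicians will be allowed to participate in multiple months", but "once a physician has been randomized to the intervention arm, they will no longer be eligible to participate in the control arm". The reverse move, from control to intervention, is not restricted.

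**Mid-month joiners (Protocol 5.1, Randomization).** A new attending "will be automatically assigned to the same randomization group as the rest of their team". No exception is made for one who has already been in the intervention arm. Section 5.1 also says that "attendings rotate approximately every 2 weeks", so a monthly team normally has two attendings and about half of attending blocks fall under this rule.

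**Allocation.** Section 5.1 randomizes physician teams "on a rolling basis for 12 months with 2 physician teams randomly selected at each site each month for participation (1 intervention, 1 control"). Section 5.2 gives a different figure for the Houston site: two teams per arm per month. Replacement of a team is described only for an attending's refusal.

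**Who is observed.** Section 5.2 states that "The primary participants are the attending physicians on each team". Physicians who decline are still observed under a waiver of consent. Section 5.1 has the analyst assign observations to an arm from the team or unit name.

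**Sustainability (Protocol 5.1).** For physicians, "select hand hygiene observations at 3 to 12 months post-intervention (based on team schedules) will be conducted".

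**Analysis.** The Protocol 5.6 hand hygiene models "will incorporate clustering by physician team (and separately for nursing unit"). The SAP names Fisher's exact test and a t-test for hand hygiene and states no clustering. Its clinician-level random effects are described for survey responses.

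**The concern.** The bar in section 5.4 evidently exists to keep trained attendings out of the control arm. The mid-month rule in section 5.1 undoes it for roughly half of the attending blocks, and nothing says which rule prevails. There is also a gap in wording: section 5.4 speaks of physicians who were randomized to intervention, whereas a mid-month joiner is assigned with the team. It is unclear whether such a joiner triggers the bar later.

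Declaring the attending ineligible would not settle the matter. The team continues to be observed and its data carry the team's arm, so a trained attending on a control team would be recorded as control. That pulls the arms together. In the other direction, intervention blocks become a growing mixture of first and repeat exposure.

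Two further consequences follow. A control attending who enters intervention later in the year may be observed for sustainability after that, with no rule on how to count the data. And an attending who serves in two months falls into two team clusters, so the hand hygiene model treats the two blocks as unrelated. Attendings carry particular weight: physician hand hygiene duration, a primary Aim 1 outcome, is measured only in attendings.

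**Working it through.** The plan gives no figure for re-entry or prior exposure, so there is none to reproduce. The 79.8% power in section 5.6 does not address this point. All sizes below are illustrations.

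**Inputs from the documents.** 12 months; one team per arm per site-month (5.1); two attendings per team-month (rotation about every 2 weeks, 5.1); targets of about 30 and 40 attendings at the two sites (5.1); 35 attendings per arm (5.2).

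**Assumptions.** The targets are used as the whole service roster, each attending is equally likely to be on service, and nobody refuses.

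**1. Prior exposure among intervention blocks.** With *m* intervention blocks per site-month and a roster of *A*, the chance that an attending has had none of them in *j* earlier months is q^j, with q = 1 - m/A. The average share with prior exposure over 12 months is 1 - (1 - q^12) / [12(1 - q)].

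| Roster A | m | q^12 | Average share with prior exposure |
|---|---|---|---|
| 30 | 2 | 0.437 | 1 - 0.563/0.800 = 30% |
| 40 | 2 | 0.540 | 1 - 0.460/0.600 = 23% |
| 45 | 2 | 0.580 | 1 - 0.420/0.533 = 21% |
| 120 | 2 | 0.817 | 1 - 0.183/0.200 = 9% |
| 40 (5.2 allocation) | 4 | 0.282 | 1 - 0.718/1.200 = 40% |

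The share grows with time. In month 12 it is 1 - q^11, or 53% for a roster of 30 and 43% for 40. Simulation that also let service frequency vary (coefficient of variation up to 0.5, 4 or 8 teams on service) gave 24-34% for rosters of 30 and 40. Rosters of 45 and 120 are included because pools of about that size are needed to yield roughly 30 and 40 distinct participants.

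**2. Cross-check from the plan's own targets.** 12 months x 2 sites x 1 team x 2 attendings = 48 blocks per arm. With 35 attendings per arm, 48 - 35 = 13 blocks are repeats, or 13/48 = 27%. This assumes that every block is filled by a participant.

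**3. Rule conflict in control.** The second attending of a control team has about the same chance of prior exposure: 12 x 0.296 = 3.6 and 12 x 0.234 = 2.8 team-months per site, or about 3-4 of 12. Rosters of 45 and 120 give 2.5 and 1.0. The section 5.2 allocation gives about 9 of 22 in Houston (simulation). In addition, about 4-7 control draws per site-year hit a team whose initial attending is already barred, a case for which no procedure is described.

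**4. Control attendings who cross over.** In simulation, 24-38% of control attendings later entered intervention. This is the share who ever cross, not the share of sustainability observations made after crossing, which cannot be worked out from the documents.

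**5. Repeat blocks and variance.** Blocks per attending are 48/35 = 1.37. With within-attending correlation r and equal repeats, the design effect is 1 + (1.37 - 1) x r: 1.04 at r = 0.1 and 1.15 at r = 0.4. With uneven repeats (CV 0.6) it is 1 + (1.36 x 1.37 - 1) x r: 1.09 and 1.35. Section 5.6 gives 0.4 for site, team or unit, not for repeat blocks by one attending, so it serves here only as an upper illustration.

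**The case against.** The strongest reply is that the one-way bar is sensible. Learned mindfulness cannot be withdrawn, so a trained attending should not serve as a control, while an untrained control attending can validly enter intervention later. Section 5.4 openly permits repeat participation, so repeat exposure is arguably part of the intervention as delivered. This stands. The bar is not an error in itself; what is missing is its reconciliation with the mid-month rule and its handling in the analysis.

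Second, the sizes depend on rosters that the documents do not give. The 30 and 40 are recruitment targets. This also stands, which is why the range is wide.

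Third, the variance figures have a limited reach. They concern attending observations; attendings are 35 of 107 physicians per arm, and nurses are unaffected. Attendings who appear in both arms induce positive covariance between the arm means, which partly offsets the inflation in the treatment contrast. So it is not established that the standard error of the overall contrast is too small. The dilution by other staff does not apply to physician duration, which comes from attendings alone.

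A reader might also infer that control attendings are selected on how often they serve. The documents give no service frequencies, and when frequency was varied in simulation the arms differed by only about 2-5% in mean service frequency. What is supported is a difference in prior exposure.

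**Conclusion.** The point holds in limited form. Sections 5.1 and 5.4 conflict for mid-month attendings with prior intervention exposure and are silent on initial attendings in the same position. As written, such an attending can supply data labelled control, the arms diverge in prior exposure over the year, and control attendings who cross over can remain control at 3 to 12 months.

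If the recruitment targets are the service rosters, with one team per arm per site-month, about 23-34% of intervention attending blocks and 3-4 of 12 control team-months per site are affected. Block shares fall to about 9-21% with larger rosters and rise to about 40% in Houston under section 5.2.

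For hand hygiene, repeat blocks by one attending are not linked. The design effect on attending observations is probably modest: 1.04 to 1.15 with equal repeats, higher with uneven ones, and partly offset in the contrast.

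Two stronger readings are not supported. One is that repeat attendings are treated as independent throughout: the SAP survey models carry clinician-level random effects. The other is that the bar must apply to both arms: that would shrink the pool and end repeat participation that section 5.4 allows, so it is a trade-off rather than a correction.

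**What to change.** 1. **Reconcile Protocol 5.1 and 5.4.** State what happens when an attending with prior intervention exposure joins a control team mid-month, or is the initial attending of a team drawn for control, and how that attending's observations are labelled. State whether assignment as a joiner counts as randomization for the bar. Settle the teams per month in sections 5.1 and 5.2 at the same time, since the frequency of the conflict depends on it.
2. **Account for attending as well as team in the hand hygiene models**, in both documents. Section 5.1 already places a unique physician study ID on the observation form. This must be reconciled with the statements in the section 5.1 risks text and in section 5.2 that the observation data carry only team or unit and role.
3. **Pre-specify two restrictions.** First, a sensitivity analysis limited to attending blocks with no prior intervention exposure. Second, exclusion of a control attending's sustainability observations made after that attending enters intervention.

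The cost is wording plus one derived exposure-history variable, provided that the physician ID is retained. The restricted analyses are less precise: on the rosters of 30 and 40, about 66-77% of intervention attending blocks remain (1 - 0.34 to 1 - 0.23), and the blocks lost come mostly from later months. That is a reason to keep it as a sensitivity analysis beside the full comparison.

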5.5 Study Evaluations

The following evaluations will be conducted. Details can also be found in section 5.1 - Study Design.

Field observational data collection will include hand hygiene adherence and duration using standardized templates for data collection (**Appendix A**). Collected data will be transferred from the paper observation data tool into a study database.

All participants will be asked to complete a survey containing validated scales measuring dispositional mindfulness, well-being, and hand hygiene perceptions. The FFMQ⁷⁵ is a validated instrument with favorable psychometric properties and consists of 39 questions. Additionally, participants will be asked to complete the WBI. The 9-question WBI assesses distress across a variety of dimensions including fatigue, depression, burnout, stress, and quality of life, and has been validated for use in physicians,⁷⁶ residents,⁷⁷ and nurses.⁷⁸ Participants will also be asked to complete 8

questions on HAI and hand hygiene perceptions selected from the PSHW developed by the World Health Organization.⁷⁹ Similar to other studies on hand hygiene perceptions guided by the constructs based on the Theory of Planned Behavior,⁸⁻¹⁰ the selected PSHW questions cover behavioral, normative, and control beliefs, as well as self-reported hand hygiene adherence. Participants will also be asked whether they meditate or perform any form of internal reflection prior to the study, as this may influence performance during the intervention. Questionnaire completion will take approximately 10 minutes. No personal identifiable information will be collected. Paper survey distribution will be used wherever feasible, but electronic versions using Qualtrics will be available for physicians that have rotated to locations outside of the VA. Study participants will be directed to a link to the survey tool (for the pre- and post-intervention, as well as 6-month post-intervention follow-up periods) and responses will be saved to a database managed by the study team.

Participants from the intervention groups will receive both independent and group-facilitated mindfulness education, will be encouraged to use a mindfulness mobile app as a practice reminder and additional resource, and instructed to integrate moments of mindfulness with repeated episodes of hand hygiene during the course of caring for patients. The control groups will receive no such education or intervention and will continue usual care.

Details of each intervention component and measures of fidelity are as follows:

- Participants will be asked to complete self-directed, online mindfulness training modules developed by the Ohio State University Mind-Body STREAM program. The mindfulness training will include three modules: (a) Introduction to Mindfulness, (b) Mindfulness in Daily Life, and (c) Mindful Breathing and Sitting. Participants will be given a unique code to use to access these training modules. The modules will not store or collect any personal identifying information. Consultant [name] will share access data with the Ann Arbor project staff by that access code which will be used to measure fidelity to the intervention.
- As part of the self-directed component participants will be encouraged to use the VA Mindfulness Coach or Mindfulness for Clinicians mobile app. Participants can choose to download this app to their personal devices. Co-investigator [name] at the VA Palo Alto Healthcare System will collect de-identified data on app usage and share with the Ann Arbor team to measure fidelity to the intervention. The mobile app does not collect any personal identifiers.
- The group-facilitated component will include discussions focused on how principles of mindfulness can be used to influence a clinician's state of mental presence, allowing for moments of clarity, insight, and reflection, and potentially enhanced provider and patient safety. Discussions will also address questions and feedback on the self-directed components discussed above. For physician participants, group-facilitated discussions lasting approximately 15 minutes will be offered every other week throughout the intervention phase at each site. For nurse participants, group-facilitated discussions lasting up to 30 minutes will be offered every week throughout the intervention phase at each site. In addition to

recording these discussions for use in the qualitative study evaluation, attendance at these discussions will be recorded to assess fidelity.

